### **4 SELECTION AND ENROLLMENT OF PARTICIPANTS**

Facilities will be randomized to either the control arm or the intervention arm. This selection will take into account the choice of each organization considering half the organizations facilities are included in each arm.

The focus of the ACP Specialist will be patients with ADRD who reside in the nursing homes during the initiative, though other patients residing in the nursing home may benefit from it in keeping with the spirit of a pragmatic trial. Only patients with ADRD will be included in the analysis. ADRD is defined to include cognitive impairment or a documented diagnosis of dementia in the MDS. Patients will be excluded if they are currently enrolled in hospice at the start of the intervention period.

Eligible facilities who agree to participate in the trial will be stratified at two levels: corporate ownership (Signature HealthCARE and Miller's Health Systems) & average number of hospital transfers per 1000 person-days alive using 2017 MDS data provided by CMS. Facilities will be grouped into low versus high hospitalization rates, using the median rate for the nursing home system as the threshold value for dichotomization. Facilities will be randomized to the intervention or control within each strata at a 1-to-1 ratio. Specifically, randomization will occur at the facility level, meaning that all patients with ADRD in the intervention buildings are eligible for inclusion in the trial. Following random assignment, we will use all available facility and patient-level data to test the balance of the intervention and control arms.

Nursing home characteristics will be obtained from nursing home corporate partners and the MDS. Potentially eligible nursing homes will be reviewed by the Data Management and Analysis Workgroup in preparation for potential inclusion in the pragmatic cluster RCT. Problematic or unstable facilities will be removed in consultation with nursing home corporate leaders prior to randomization.

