## **6 STUDY PROCEDURES**

### **6.1 Description of Evaluations**

#### 6.1.1. Enrollment, Baseline, and/or Randomization

Nursing home Eligibility: All Medicare-certified nursing homes are eligible at Signature HealthCARE and Miller's Health Systems.

Nursing home Recruitment & Characteristics:

The ACP Specialist Program will be rolled out as a corporate initiative and nursing home Executive Directors will be requested to participate in the initiative by nursing home corporate leadership. It is anticipated all nursing home Executive Directors who are approached will agree to participate.

Nursing home corporate partners each provided data about key nursing home characteristics. At the time of randomization Signature HealthCARE owns 109 nursing homes in 8 states, with a total of 8,811 beds; 43% are rural. Miller's Health Systems owns 33 nursing homes, all in Indiana with 3,066 beds; 55% are rural. The mix of rural and urban facilities will provide a rich environment for this pragmatic trial. Self-reported 30-day hospital readmission rates for 2016 range from 13% for Miller's Health Systems and 17% for Signature HealthCARE nursing homes.

Random Assignment: Nursing homes will be sorted into groups that are comparable on hospital transfer rates. Eligible facilities who agree to participate in the trial will be stratified at two levels: corporate ownership (Signature HealthCARE and Miller's Health Systems) & average number of hospital transfers per 1000 person-days alive using 2017 MDS data. Facilities will be grouped into low versus high hospitalization rates, using the median rate for the nursing home system as the threshold value for dichotomization. Facilities will be randomized to the intervention or control within each strata at a 1-to-1 ratio. Specifically, randomization will occur at the facility level, meaning that all patients not currently on hospice at the start of the intervention period in the intervention buildings are eligible for inclusion in the trial. The intervention focuses on patients with ADRD, but other residents of intervention facilities are not excluded. Following random assignment, we will use all available facility and patient-level data to test the balance of the intervention and control arms.

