### **9.3 Interim analyses and Stopping Rules**

We will not be conducting an interim analysis or developing rules for stopping the trial early for several reasons. The planned intervention of a trained ACP Specialist who will augment usual care is unlikely to cause harm. The IRB has determined that this study is minimal risk. Particularly given the delay in obtaining Medicare claims for determining the primary outcome, hospitalization or emergency department visits, it will not be feasible to determine the differences in this outcome between the intervention and control groups until the end of the 12 month outcome observation period.

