### **9.4 Outcomes**

#### **9.4.1 Primary outcome**

9.4.1.1 Hospital transfers over 12 months among ADRD patients

#### **9.4.2 Secondary outcomes**

9.4.2.1 Hospice enrollment over 12 months among ADRD patients

9.4.2.2 Death in hospital over 12 months among ADRD patients

### **9.5 Data Analyses**

Design consideration. The R33 phase of the study has two aims: (Aim 1 – Primary) To compare hospital transfers (admissions and emergency department visits) over 12 months between ADRD patients in the intervention and control facilities; and (Aim 2 - Secondary) assess the interventional effect of the ACP Specialist Program on hospice enrollment and place of death. Towards these ends, we employ a cluster RCT design. With this design, randomization will be carried out at the nursing home level, stratified by nursing home corporate ownership and baseline hospitalization transfer rates (low versus high). All patients at a given nursing home will have the same intervention assignment. The trial outcomes will be analyzed at the individual patient level and reported at the facility level. The cluster RCT with nursing home randomization is chosen because of its ability to simultaneously maximize the implementational feasibility and minimize the contamination risk. Counts of hospital transfers and emergency department visits incurred by individual ADRD patients during the follow-up period will be considered as the primary outcome. We designed the trial to ensure adequate power for the hypothesis concerning the primary outcome. Average age and proportion of female patients is similar across our nursing home partner facilities and the U.S. The % of Black patients ranges from 6-17% across the population of our partner nursing homes. About half of nursing home patients have a dementia diagnosis. This is similar for our partner facilities.

Analysis will be carried out in an intention-to-treat (ITT) framework, which gives a pragmatic estimate of the interventional benefit. The ITT analysis will use data from all eligible patients in randomized facilities, regardless of the level of facilities' adherence to the study protocol and patient attrition. ITT is a preferred approach for pragmatic trials

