because the analysis generates estimates of treatment effectiveness in a more realistic way. In fact, clinical effectiveness can be severely overestimated if ITT analysis is not performed. Within the ITT framework, we propose to analyze the trial data using appropriate generalized linear models. Specifically, we plan to compare the rates of hospital admissions in patients residing in the intervention vs control facilities. In line with intention-to-treat principles and our cluster randomized design, hospitalizations will be analyzed at the facility level, including for residents who moved across intervention and control buildings during the study period. Group assignment will be based on the facility each resident was first admitted to during the intervention period. Thus, some residents may have a documented ACP encounter in intervention facilities but also spent some time in control facilities. The analysis will be carried out using an appropriate count data regression model, length of observation will be adjusted as an offset parameter. We will test the levels of extra-Poisson variation to determine if a Poisson regression model is sufficient for the analysis. If the level of variation is beyond what can be accommodated by the Poisson model, we will consider using negative binomial regression. Similarly, we will test the presence of extra zeros that beyond the Poisson or negative binomial models. If necessary we will consider the use of zero-inflated Poisson or negative binomial regression analysis. Correlations among outcomes measured from residents in the same facility will be accounted for by adding random facility effects into the regression models. This analytical approach handles missing data (early dropout due to death or transfer to hospice) more easily because of the inclusion of offsetting parameters in the model.

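### Section 9.5 treats transfer to hospice as dropout handled by the offset, with no individual rule for when observation ends or whether later transfers count

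*Combined protocol and SAP*

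**What the plan says.** The primary outcome in Section 9.5 is "Counts of hospital transfers and emergency department visits incurred by individual ADRD patients during the follow-up period". It is analysed by Poisson or negative binomial regression, zero-inflated if needed, with random facility effects, and "length of observation will be adjusted as an offset parameter". The only sentence on hospice in the primary analysis is: "This analytical approach handles missing data (early dropout due to death or transfer to hospice) more easily". The reason given is that the model includes offsets.

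On length of follow-up, the Précis, Section 3, Section 9.3 and Section 9.4 all give 12 months; Section 9.3 speaks of waiting "until the end of the 12 month outcome observation period". The implementation period is 18 months. No index date is given for a resident within it.

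On the analysis set, Section 9.5 states: "The ITT analysis will use data from all eligible patients in randomized facilities". It adds that this holds whatever the patient attrition.

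On hospice, Section 1.2 hypothesises greater enrollment in intervention homes, and Section 9.4.2 makes enrollment and death in hospital secondary outcomes over 12 months. Sections 4, 4.2 and 6.1.1 exclude residents who are on hospice at the start of the intervention period.

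**The concern.** If hospice entry is dropout, a resident's events and person-time stop on the day of entry. That event follows randomisation, and the trial expects more of it in one arm. It also differs from death, because a resident on hospice is alive and can still go to hospital.

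Two separate things then happen. First, the quantity changes: any reduction in transfers that comes through hospice use leaves the rate ratio, and what remains is a rate while not on hospice. That can be a legitimate target, but the plan does not name it and describes a 12-month intention-to-treat comparison. Second, the truncation can be informative: if residents with high transfer rates enter hospice sooner, and more of them do so in intervention homes, high-rate person-time is removed from that arm. The offset deals with neither.

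Because the rule is implied and not written, two analysts following Section 9.5 could also use different events and different person-time for the primary outcome.

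**Working it through.** **Passages side by side.** Toward stopping at hospice: the word dropout in Section 9.5. Toward continuing: 12-month follow-up of all ADRD patients (Section 3), intention-to-treat regardless of attrition (Section 9.5), and death in hospital over 12 months (Section 9.4.2), which for hospice enrollees needs follow-up after entry. The stratification rate in Section 4 is the "average number of hospital transfers per 1000 person-days alive using 2017 MDS data provided by CMS", with no stop at hospice. On data, Section 9.3 cites the "delay in obtaining Medicare claims for determining the primary outcome", so hospice entry does not by itself end capture. Section 13 still plans checks that all transfers are captured.

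**The plan's own figure.** The plan gives no figure on hospice. Section 9.2 states 81% power for 1.0 versus 0.8 per resident-year, with 60 homes per arm and 50 residents each. The between-home CV used is not stated, only that it is below 0.5. At CV 0.40, power = Φ(0.2 × √[59 / (1.8/50 + 0.16 × 1.64)] − 1.96) = Φ(0.85) = 80%; the log-rate scale gives 81.6%. This is a back-solved match (at CV 0.50 power is 63–65%). At CV 0.40 with 0.8 person-years per resident, power is about 79%. Shorter observation therefore costs little power; the issue is what is estimated.

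**Model for the rate ratio.** All inputs are assumed, because the documents give none:
- pre-hospice mortality d0 = 0.25 per year;
- hospice entry h = 0.20 (control) versus 0.25 or 0.30 (intervention), which is 16% versus 20–23% enrolled within a year;
- mortality after hospice entry d1 = 0.25, 1.5 or 3.0 per year;
- transfer rate on hospice = r × the pre-hospice rate, r = 0.1 to 0.3;
- no programme effect before hospice.

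Tpre = (1 − e^−(d0+h)) / (d0+h)

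Tpost = ∫₀¹ h e^−(d0+h)s × (1 − e^−d1(1−s)) / d1 ds

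Full rate = (events before + r × events after) / (Tpre + Tpost). Censored rate = events before / Tpre.

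Example with h = 0.20 versus 0.30, d1 = 1.5, r = 0.1, pre-hospice rate 1:
- Control: Tpre 0.8053, Tpost 0.0547; full rate = 0.8107/0.8600 = 0.943.
- Intervention: Tpre 0.7692, Tpost 0.0793; full rate = 0.7771/0.8485 = 0.916.
- Full ratio = 0.972; censored ratio = 1.000.

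Frailty is added as a mean-1 log-normal factor on both the hospice and transfer hazards. In the same example with log-SD 0.7, full is 0.955 and censored 0.978. With r = 1, full is 0.994 and censored 0.978.

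Censored minus full ratio, in points (0.01 on the ratio), over both values of h:

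| d1 | No frailty, r 0.1–0.3 | log-SD 0.4, r 0.1–0.3 | log-SD 0.7, r 0.1–0.3 | log-SD 0.7, r = 1 |
|---|---|---|---|---|
| 0.25 | +1.5 to +4.0 | +1.4 to +3.8 | +1.0 to +3.3 | −1.1 to −2.2 |
| 1.5 | +1.1 to +2.9 | +1.0 to +2.7 | +0.7 to +2.4 | −0.8 to −1.6 |
| 3.0 | +0.8 to +2.0 | +0.7 to +1.9 | +0.5 to +1.7 | −0.6 to −1.1 |

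The first numeric column isolates the change in estimand. The last isolates informative truncation, because r = 1 means hospice does not alter transfers. The difference changes sign at r of about 0.62 (log-SD 0.7) or 0.85 (log-SD 0.4).

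**A second set of assumptions**, without frailty: hospice hazards matching 20–30% (control) versus 30–45% (intervention) at 12 months, r = 0.2–0.5, mortality 0.2 before and 0.7–1.4 after entry. The ratio is 1.00 if both events and time stop at hospice, 0.92–0.98 if both continue, and 0.89–0.96 if events stop but time runs on. Wider hospice differences thus enlarge the gap to 2–8 points, and using different end rules for events and offset adds a further shift.

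**The case against.** **Follow-up is not undefined.** A reader might infer that the plan never says how long follow-up lasts. That is too strong: 12 months is stated repeatedly. What is missing is the index date and the individual end rule.

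**The baseline exclusion fits a non-hospice rate.** Leaving out residents already on hospice is compatible with a rate while not on hospice. It defines who enters the cohort, however, and does not settle what happens when someone enrolls later.

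**Transfer to hospice may mean leaving the building.** MDS and EHR records could then stop, and dropout would be a natural word. This stands as an open question. Claims are a planned source for the outcome, but no section says they capture every transfer after hospice entry.

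**Some contrary evidence is weak.** The person-days-alive rate is a 2017 stratification variable, not an outcome definition. Death in hospital could have its own follow-up. Both show tension with stopping at hospice; neither proves a contradiction.

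**Follow-up to death can also depend on arm** if the programme changes survival. This is true, and continuing through hospice does not remove it. A table of reasons for end of observation by arm would make it visible.

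**The effect is modest** against a planned 20-point reduction. That also stands.

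**Conclusion.** The point holds as a gap in the definition of the primary estimand that should be fixed. The plan's wording most naturally ends observation at an event that the programme is meant to increase, and the offset cannot make that truncation non-informative. It remains an implication: the documents do not state censoring at hospice as a rule.

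Size rests wholly on assumed inputs. With transfers on hospice at 10–30% of the pre-hospice rate and a modest difference in hospice entry, the censored ratio lies roughly 0.5 to 4 points above the full-follow-up ratio, so it understates benefit relative to full follow-up.

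A reader might infer that stopping at hospice would manufacture a benefit, or that the direction is simply unknown. Neither is supported under these inputs. Informative truncation alone does pull toward a false benefit, but in every scenario in the main table with r of 0.1–0.3 the estimand change outweighs it. Reversal needs transfers on hospice at about 60–85% or more of the pre-hospice rate under the frailty values tried. Nor do the documents show that the primary conclusion would change.

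**What to change.** In Section 9.5:

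- Remove transfer to hospice from the dropout wording.
- State the index date. For both the event count and the offset, run observation from that date to the earliest of death, 12 months, or loss of claims/MDS capture, regardless of hospice enrollment.
- Report censoring at hospice entry as a labelled sensitivity analysis, with hospice entry defined as enrollment or as leaving the facility.
- Tabulate by arm the reasons for end of observation and the person-time.
- If a rate while not on hospice is intended as primary, name it as the estimand before analysis and report the full-follow-up rate beside it.

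The cost is protocol/SAP wording before analysis, one sensitivity analysis and one table. Claims and MDS are already planned sources. The validity checks in Section 13 must explicitly cover transfers after hospice entry, since the fix depends on that capture.

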## **10 DATA COLLECTION AND QUALITY ASSURANCE**

### **10.1 Data Management**

The proposed study will combine multiple sources of patient data to measure impact on the quality of care near the end-of-life.

### **10.2 Quality Assurance**

#### **10.3.1 Training**

ACP Specialists will complete standardized training via modules created for the study and available in their learning management systems. Corporate representatives and corporate implementation champions will complete a corresponding training adapted for key leaders via modules created for the study and available in their learning management systems.

#### **10.3.2 Quality Control Committee**

Not applicable.

#### **10.3.3 Metrics**

Provide quality control metrics for outcome measures.

#### **10.3.4 Protocol Deviations**

Protocol deviations will be assessed in monthly meetings with the corporate implementation champions. Since this is a pragmatic trial, we anticipate and have built-in flexibility in implementation of the ACP specialist program that would not be considered a protocol deviation.

### 10.3.5 Monitoring

Monitoring will occur via review of the monthly data transfer and through monthly meetings with the corporate implementation champions.

## 11 PARTICIPANT RIGHTS AND CONFIDENTIALITY

### 11.1 Institutional Review Board (IRB) Review

The proposed study has been reviewed by the Indiana University Institutional Review Board (IRB), which will serve as the centralized, single IRB for the trial in accordance with National Institutes of Health policy. This trial is registered at [clinicaltrials.gov](https://clinicaltrials.gov) (NCT03323502). A Data Safety and Management Plan is described in this protocol.

### 11.2 Informed Consent Forms

A waiver of informed consent was sought from the IRB. This pragmatic clinical trial meets the criteria for a waiver of informed consent as described in 45 CFR 46:116. Specifically: 1) this research represents no more than minimal risk; 2) a waiver does not adversely affect the rights and welfare of participants; 3) the research could not be practicably carried out without the waiver; and 4) information will be provided to the nursing home partners after the trial to share with interested patients and family caregivers. Patient and family caregiver refusals to participate in ACP discussion will be honored.

### 11.3 Participant Confidentiality

Data provided by nursing home corporate partners (MDS, EHR) will be transferred using HIPAA compliant, encrypted processes. CMS (Claims, MDS) and EHR data files will be securely stored using processes developed to meet CMS data requirements as part of a prior CMS data request. Specifically, data will be stored on a virtual server administered by Indiana University's Clinical Affairs IT Service (CAITS) team. The virtual server is located on Indiana University's Intelligent Infrastructure on hardware that is physically located in two enterprise-class machine rooms in separate physical locations. The server rooms require biometric authentication in addition to a chip-based access card and are staffed 24x7x365 and feature video security. Network firewall rules are used to restrict server access to only necessary subnets. Only IU domain workstations with security controls (auto logoff, centralized threat management, host-based firewall, and more) will be permitted to connect to the virtual server. Each study team member with access to the CMS data must use a passphrase. Protocols are in place dictating that passphrases must be at least 15 characters in length with at least 4 unique characters (letters, numbers, and symbols) and use at least 4 words separated by spaces or other non-letters. Password reuse is restricted, not allowing the previous 2 passwords to be reused. Sessions on workstations and servers, whether local or remote, are locked after being idle for 15 minutes and terminated after 24 hours of non-use.

The systems used to store and analyze the data will be subjected to a documented NIST-based risk management process prior to receipt and use of the requested data. The process is briefly outlined below:

- a) Inventory assets—hardware, software, personnel.

- b) Document controls—identify every existing and appropriate NIST 800-53 control for the system. NIST 800-53 (an industry and government standard) is a comprehensive catalog of 926 security controls. NIST 800-66 (a mapping of the HIPAA security rule to NIST 800-53) is used to identify appropriate controls for electronic Personal Health Information.
- c) Assess risk—identify risks that existing control address and residual risk from missing controls.
- d) Respond to risk—how each residual risk is addressed (mitigated, transferred or accepted), explanation/justification, and timelines for mitigation, if any.
- e) Establish ongoing risk management—semi-annual reviews and documentation updates, external assessments.
- f) Training—two annual HIPAA training courses (University general course and an IT-specific course).

#### **11.4 Study Discontinuation**

The study may be discontinued at any time by the IRB, the NIA, the OHRP, the FDA, or other government agencies as part of their duties to ensure that research participants are protected.

### **12 ETHICAL CONSIDERATIONS**

#### Protections against Risk

Informed consent will not be sought from patients or family caregivers for this pragmatic cluster randomized control trial. Strategies to minimize risk to participants are based on the experiences of the study PI and Co-Is in conducting research on ACP and in the nursing home setting. Additionally, [name] has expertise in ethical issues in research with these populations to inform both study design and strategies to protect against risk. [name] has previously conducted research on ethical issues in conducting long-term care research and NIH-funded research on ethical issues in end-of-life research.

